7.2 Assessment and reporting of adverse events

The occurrence of adverse events will be assessed by non-directive questioning of the participant at each visit. Further, adverse events volunteered by the participant during or between visits or detected through observation, physical examination, laboratory test, or other assessments during the observation period, will be documented. Participants will be instructed that they must immediately report any adverse events, subjective complaints or objective changes in their well-being to the study doctor or the clinic personnel, regardless of the perceived relationship between event and test product.

All AEs will be recorded by the study doctor or clinic personnel in the CRF and subject notes from the signing of informed consent until the end of the trial (3 years of treatment). The AEs will be followed until resolved, if applicable.

7.3 Reporting of serious adverse events

All serious adverse events (SAEs) are to be recorded in the CRF and subject's notes from the signing of informed consent until the end of the trial (after 3 years of treatment).

SAEs must be reported immediately to the sponsor. The study doctors or clinic staff are required to notify the sponsor by completing the Serious Adverse Event template and emailing or faxing the sponsor, within 24 hours of them becoming aware of the occurrence of a serious adverse event. The sponsor is responsible for notification to the appropriate authorities, if applicable (A serious adverse event reporting form template must be prepared and made available to the investigators for quick reporting).

All SAEs should be reported promptly to the REC, if applicable in accordance with the International Conference on Harmonisation Good Clinical Practice (ICH GCP) E6, (Section 4.11.1). The SAE will then be followed until resolved, if applicable.

If the SAE was unexpected, it is then defined as a Suspected Unexpected Serious Adverse Reaction (SUSAR) and should be reported by the sponsor to the MHRA and relevant REC. If the SUSAR is fatal or life threatening, then these should be reported immediately and at least not later than seven days after the sponsor was first aware of the reaction. Any additional relevant

information should be sent within eight days of the report. Electronic reporting will be adopted using the MHRA's eSUSAR website, the EudraVigilance Gateway or EVWEB. The sponsor shall keep detailed records of all adverse events relating to the clinical trial which are reported to it by the study doctors or clinic staff for the trial. The Licensing Authority may require the sponsor to send those records, or copies of such records, to the authority. For all other SUSARs the sponsor must inform the MHRA and relevant REC within 15 working days of them becoming aware of the SUSAR.

7.4 Actions to be undertaken

The responsible study doctor will initiate appropriate treatment according to his/her medical judgment and will decide whether to withdraw the subject from the study if an adverse event or a concurrent health condition occurs. The subject must be followed-up by additional examinations according to the medical judgment of the study doctor, until the abnormal condition is resolved, or the study doctor deems further observations or examinations to be no longer medically required.

7.5 Stopping Criteria

Close monitoring of the subjects during the study will be performed. Any decision to stop the study will be immediately communicated to all investigators and to the relevant regulatory authorities.

8. DATA MANAGEMENT AND QUALITY CONTROL

8.1 Case report forms and data management

An independent data management party will prepare a CRF at the time of analysis for each subject. The CRF will record the subject number which will be obtained from the subject database Heydoc which is an automatically generated subject number. No other subject personal details will appear on the CRF. The clinical personnel at the site will obtain from the Heydoc system the date that the subject entered the study and the date the subject was either removed from the study, died or the date being five years after entering the study if none of the previous dates are applicable and record this information on the CRF.

In addition, the site will obtain from the Heydoc system for each subject the scanned in external quarterly reports obtained from the subjects. The sponsor will ensure that the CRF is correctly completed. The CRF will be signed by the investigator signifying agreement with and responsibility for the recorded data.

A list of all data fields to be recorded in the CRF, will be generated by the sponsor and which documents are the sources for that data (i.e. the source documents) and which data, can be directly entered into the CRF.

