Unacceptable contraception methods:	Periodic abstinence (calendar, symptothermal, post-ovulation methods), withdrawal (coitus interruptus), spermicides only, and lactational amenorrhoea method (LAM) are not acceptable methods of contraception. Female condom and male condom should not be used together.
Women of child bearing potential:	For the purpose of this document, a woman is considered of childbearing potential (WOCBP), i.e. fertile, following menarche and until becoming postmenopausal unless permanently sterile. Permanent sterilisation methods include hysterectomy, bilateral salpingectomy and bilateral oophorectomy. A postmenopausal state is defined as no menses for 12 months without an alternative medical cause. A high follicle stimulating hormone (FSH) level in the postmenopausal range may be used to confirm a post-menopausal state in women not using hormonal contraception or hormonal replacement therapy. However, in the absence of 12 months of amenorrhoea, a single FSH measurement is insufficient.
End of the trial:	The length of the trial for each participant is a maximum of 3 years.

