data will trigger automatic alerts to clinicians who will contact those subjects for assessment. Subjects will have quarterly consultations with specialists to discuss their treatment and to collect adverse events, until the end of the 3 years of treatment. On each 3 monthly follow up, an updated medical history will be taken, alongside information on current standard of care treatment and a review of the CBMP prescribed will be undertaken (see figure 1).

Under the supervision of an appropriately qualified and trained physician, all subjects will be prescribed a dose of CBMP product that is appropriate for their type of chronic non-cancer pain, their medical history and their previous experience with cannabis. Cannabis tolerance will be monitored via ePRO data collection with tolerability questions asked after each vapourisation session. After 1 month of treatment at the low dose, this information will be used, alongside regular monitoring of the subject, to guide the Investigator on whether the subject can be titrated to the higher dose. The length of the trial for each participant is 3 years. Treatment will continue until the end of the study (see figure 1). An overview on the study procedures is given in the schedule of assessments (Table 1-1).

Figure 1; schematic of patient journey

Stage 4	
Clinic treatment phase
 
Predominantly application-based data collection, video consultation/face-to-face reviews at 3-month timepoints. Review tolerability, treatment effects and concomitant changes to standard of care
 
Patients asked if they want to join CANPAIN study and are provided with PIS about study and draft study consent form.
 
If they want to enter study inclusion/exclusion criteria confirmed and meeting arranged to review study consent form and get it signed.
 
Study protocol followed for this patient from this point on until end of maximum of 3 years

---------	--

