6.3 Study Duration

The study duration is 3 years. Subjects will only be followed for as long as the individual investigator or individual subject agrees.

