6.5.5 Treatment after end of study

Subjects will be free to continue to receive treatment and medical care at the clinic after termination of the study, in compliance with local regulations. Those not receiving ongoing treatment at the clinic, no further follow up or data will be collected on these subjects. Any data from patients who continue to receive treatment after the 3-year study period will be outside the study and will not contribute to the study database.

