9.5.1.1 Change in baseline pain NRS

The change in baseline pain NRS will be defined as the difference between chronic pain state at the beginning of the study versus the end of the study (after 3 years of treatment).

The primary analysis will be a difference analysis with comparison to appropriately selected matched controls. The endpoint will be tested using a two-sided z-test test to compare results between the prospectively enrolled treated participants and external matched controls. The impact of confounding factors will be reduced as much as possible by including values of important covariates in the model and by performing sub-analyses. Covariates included in the model will be selected based on:

- (1) Base line pain scores
- (2) Cannabis consumption experience and/or
- (3) Cause of chronic pain

A propensity score analysis may also be performed to match subjects between the treated and matched control groups. The propensity score is the probability of treatment assignment conditional on observed baseline characteristics. Propensity score matching entails forming

matched sets of treated and untreated participants who share a similar value of the propensity score (Rosenbaum PR & Rubin DB, 1983a and 1985).

Secondary measure outcome variables

Descriptive statistics will be presented for Quality of life changes, sleep NRS changes, Anxiety changes, confusion changes, dizziness changes, and changes in the use of concomitant medicines. Change from baseline to a number of analysis time points (including 12 months) will be assessed. Repeated measures analyses will be undertaken to allow for the evaluation of outcomes at any timepoint. In addition, multi-state modelling (MSM) will be undertaken to assess time-varying confounds. These will be described in detail in the SAP.

A comparison between treated subjects and matched control may be performed if similar endpoints are collected in both databases. Time to event analysis, multiple regression analysis for continuous and/or categorical outputs and/or propensity score analysis may be performed as appropriate.

To deal with missing data in subjects over the 3 year period, patterns of missingness will be evaluated including missing completely at random (MCAR), missing at random (MAR) or missing not at random (MNAR) will be assessed, this will be described in detail in the SAP.

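### The draft main-study protocol dates a completer's exit at five years after entry, although participation ends at three, so any follow-up or censoring time taken from that CRF field would be overstated

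*Protocol*

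**What the plan says.** The rule is in section 8.1 (Case report forms and data management) of the draft CANPAIN protocol appended to the feasibility protocol. Site staff take two dates from the clinic database: the date of entry and a date of exit. The exit date is the date of removal or of death, and otherwise "the date being five years after entering the study if none of the previous dates are applicable".

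The rest of the draft gives three years per subject:

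- Section 3.1, under end of the trial: "The length of the trial for each participant is a maximum of 3 years".
- Section 6.1: "The length of the trial for each participant is 3 years", with quarterly reviews up to that point.
- Section 6.3: "The study duration is 3 years".
- Section 6.5.5: "Any data from patients who continue to receive treatment after the 3-year study period will be outside the study".
- Sections 7.2 and 7.3: adverse events and serious adverse events are recorded from consent to the end of three years of treatment.
- Section 9.5.1.1: the change in pain score runs from the start of the study to three years of treatment.
- Synopsis: treatment duration is three years.

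Two sections describe analyses for which a duration might be needed. Section 9.5.1.1 lists "Time to event analysis, multiple regression analysis for continuous and/or categorical outputs" among methods that may be applied, and section 9.5.2.2 says that exposure to the regimen will be summarised.

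**The concern.** For a subject who is neither removed nor dead, the CRF would show an exit two years after the last point at which the protocol observes anyone. These are the only entry and exit dates that section 8.1 puts on the CRF, so a programmer looking for time in study would naturally subtract one from the other. If that is done, subjects are credited with event-free or exposed time during which nobody was collecting data. The error goes one way only: durations become too long, and a censoring time falls after the last observation.

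**Working it through.** **Inputs**

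| Quantity | Value | Source |
|---|---|---|
| Default exit date | entry + 5 years | section 8.1 |
| Maximum participation | 3 years | sections 3.1, 6.1, 6.3, 6.5.5, 7.2, 7.3, 9.5.1.1; synopsis |
| Share of completers, *f* | 0.30 to 0.70 | assumed; not in the protocol |
| Mean follow-up of non-completers, *m* | 0.5 to 1.5 years | assumed; not in the protocol |

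**Could the five years be explained by staggered entry?** No. They run from each subject's own entry, as do the three years in sections 3.1 and 6.1.

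**Can the date be observed within the study?** Section 6.1 ends the study after the last subject's three years. That subject's default exit date falls 5 − 3 = 2 years later. Section 11.4 has the report summary sent within one year of the end of the trial, so the date would fall at least 2 − 1 = 1 year after it was due.

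**Per completer**

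- Excess: 5 − 3 = 2 years.
- Ratio of recorded to observed time: 5/3 = 1.67, or +67%.

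**Over all subjects**, if non-completers have correct dates:

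- Observed mean time: T = 3f + m(1 − f)
- Recorded mean time: R = 5f + m(1 − f)
- Overstatement: R/T − 1 = 2f/T

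| f | m = 0.5 | m = 1.0 | m = 1.5 |
|---|---|---|---|
| 0.30 | 1.85/1.25: 48.0% | 2.20/1.60: 37.5% | 2.55/1.95: 30.8% |
| 0.50 | 2.75/1.75: 57.1% | 3.00/2.00: 50.0% | 3.25/2.25: 44.4% |
| 0.70 | 3.65/2.25: 62.2% | 3.80/2.40: 58.3% | 3.95/2.55: 54.9% |
| 1.00 | 66.7% | 66.7% | 66.7% |

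A subject lost to follow-up without a recorded removal would also receive the five-year default. Section 6.4.5 promises efforts at contact but does not say what exit date follows if they fail. Such cases would raise these figures.

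**Which planned outputs could use the date?**

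| Output | Depends on the exit date? |
|---|---|
| Change in pain score (9.5.1.1) | No; fixed at three years of treatment |
| Adverse-event tables (9.5.2.1) | No; subjects counted once per term, shown as counts and percentages |
| Exposure summary (9.5.2.2) | Possibly; source not stated, and the vaporiser application also records dosing (6.5.1) |
| Time-to-event analysis (9.5.1.1) | Possibly; optional, no censoring rule in the protocol |

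**The case against.** The strongest reply is that nothing in the protocol derives a result from this date. Section 8.1 only records it, dosing is captured separately, time-to-event analysis is optional, and a censoring rule would normally be left to the statistical analysis plan. This stands, and it makes the consequence conditional.

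A reader might infer that adverse-event rates would be understated by 40%, since 3/5 = 0.60. The documents do not support that. No rate per person-year is planned, and the adverse-event denominators are numbers of subjects. The figure would also apply to completers alone.

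A reader might also infer that late entrants are affected more. That needs the study to close three calendar years after it opens, which sections 6.3 and the synopsis could suggest. Section 6.1 instead continues until the last subject has had three years, and then late and early completers are affected equally.

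It can be said that finishing at three years counts as removal, so that the default never applies. Section 6.4.5, however, uses removal for premature departure, and the default has a purpose only for those who did not leave early. Some activity does extend past treatment: a pregnancy test three months afterwards (section 6.4.3) and follow-up of unresolved adverse events (section 7.2). Neither amounts to a five-year observation period.

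The error may well be noticed, because the CRF is completed at the time of analysis and the sponsor checks it against source data (sections 8.1 and 8.2). But that check also covers adherence to the protocol, and a five-year date adheres to section 8.1.

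Finally, the rule is in a draft for a later study. The feasibility study takes its data from the electronic health record for a feasibility report, so it is not affected. This also stands.

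**Conclusion.** The contradiction is real: one operative data-recording rule says five years, everything else about participation says three, and nothing in the document supports a five-year follow-up. Each completer's recorded time in study would be 2 years, or 67%, too long. Averaged over all subjects, the excess would be about 31% to 62% under the assumed 30% to 70% completion and 0.5 to 1.5 years' mean follow-up in the others.

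These figures affect a result only if follow-up, exposure or censoring time is taken from this field, which the protocol permits but does not state. The three-year pain comparison and the subject-count safety tables are sound in this respect. This is a data-definition error worth correcting before the main study is resubmitted; it is not a flaw in the primary analysis.

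**What to change.** Reconcile section 8.1 with the three-year limit stated elsewhere. Define the CRF exit date as the earliest of:

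- withdrawal from the study,
- death,
- last study contact, for a subject lost to follow-up,
- three years after entry, or the data cut-off for a subject still in the study at an interim analysis.

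Withdrawal must mean leaving the study, not stopping treatment. Section 6.4.8 keeps following those who discontinue treatment, and ending their record at discontinuation would discard valid follow-up. If exposure is to be calculated from dates, it needs its own treatment-stop date.

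The cost is one line in section 8.1 and the matching CRF field definition. No treatment, visit or follow-up rule changes, and no data need be re-collected.

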8.2 Quality control

The study will be supervised by the sponsor. The sponsor will contact the clinical trial site regularly to discuss the progress of the study and to check the study documents including the informed consent forms for completeness and consistency.

The sponsor will verify the data entered in the CRF at the time it has been recorded on the CRF with the source data at the study centre in order to confirm accuracy and adherence to the study protocol.

The Heydoc system which records all the subject data and stores all the subject information and documents is an externally run and controlled database that has been audited and verified as being acceptable for medical record keeping, data protection and back up and access purposes. Every user has their own log in details and passwords that have to be changed every month. Any change made to the system is recorded by the person making such change and every change is auditable and non-removable so that any changes can be tracked and verified.

Heydoc is the online practice management software solution, which has been designed and developed by Heydoc.

Heydoc is one of the leading online system available on the UK market, and the only full-service solution that enables single and multiple location private medical practices to connect securely to their data from any location worldwide.

The data is stored at a high security and internationally approved data centre based in the United Kingdom. Hardware is monitored 24/7 in a temperature-controlled environment with a battery and generator standby for use in the event of power failure. The Heydoc technology creates a secure connection that transports data entered by authorised users through the World Wide Web, allowing protection from viruses, spy ware, SPAM, and other unwanted Web browser traffic. The system operates in the same environment commonly used by Banks and UK Government departments to handle information transfers. All data transmitted through Heydoc is encrypted using Secure Socket Layer (SSL), the highest form of internet data encryption. Algorithms scramble data so that unauthorized users cannot view it, keeping all subject data safe from data pirates or hackers.

Heydoc is registered as a Data Controller with the Information Commissioners Office and is subject to the Data Protection Act. The company is accredited by Lloyd's Register Quality Assurance to ISO27001 standards and complies with NHS Information Governance Statement of Compliance (IGSoC).

9. STATISTICAL METHODS AND DETERMINATION OF SAMPLE SIZE

9.1 General considerations

The aim of the study is to evaluate whether a medical cannabis treatment in addition to standard of care is beneficial with regards to pain scores, quality of life measures, sleep scores, changes in concomitant medication use, subject's global impression of change and general wellbeing score, as well as being safe and tolerable. The study is a non-randomised, non-blinded, single arm study with comparisons being made against matched control database(s) where available and applicable.

There are many causes of chronic pain, which can be described as either neuropathic or non-neuropathic. In addition to those two main subtypes, there are 10 further subtypes which are as follows: systemic inflammatory disease, osteoarthritis, lower back pain, inflammatory bowel pain, neurogenic pain, post cancer pain, post trauma pain, psychogenic pain, genitourinary pain and vascular pain. These pain types will be recruited into both the CANPAIN cohort and matched cohorts.

The use of matched controls instead of a randomised control design is the best approach to studying medicinal cannabis due to the inherent difficulties of blinding trial subjects to the effects of cannabis. Protocol designs for the study of medicinal cannabis have been recently reviewed in a BMJ editorial (Freeman and Morgan 2019) which support the use study designs such as ours in the generation of evidence in medicinal cannabis use. Subjects in the active and control cohorts will be matched on a range of demographics, socio-economic, pain, and health related variables (see response to comment 1d). Certain covariates (such as gender) may be considered for exact matching if appropriate. Subjects will be matched using an optimal matching algorithm. For the primary analyses, a 1-1 matching algorithm will be used. At a predefined interval (12 months), a multiple regression analysis will be undertaken on subjects in the matched control cohort to assess which co-variables (e.g. categories of standard of care, pain type or location of pain). are important for the matching process with the CANPAIN cohort. Subgroups of special interest include type of pain, inclusion of gabapentinoids, age and gender. Subgroups of exploratory interest include but are not limited to, standard of care, site of pain and prior cannabis use. These will be fully defined in the SAP.

Full details, including the use of the matched control database(s), of the interim and final statistical analyses to be performed will be described in detail in the Statistical Analysis Plan (SAP). The SAP will be developed to specify the statistical methods to be used and it will be finalized prior to the final or interim data cut-offs.

The progress of each subject identified for participation in the trial will be documented in a flowchart so that all subjects are accounted for, whether or not they go on to enter the trial itself. This flowchart will also show the number of subjects with data available as well as the incidence of withdrawal from treatment. All data obtained in this study will be presented in individual subject data listings.

The analyses will be exploratory and primarily make use of descriptive statistical methods. Tabulations will be produced for appropriate effectiveness and safety parameters. For categorical variables, summary tabulations of the number and percentage of participants within each category (with a category for missing data where applicable) of the parameter will be presented. For continuous variables, the number of participants, mean, standard deviation (SD), median, minimum, and maximum values will be presented. Statistics may be presented for cohorts of interest (e.g. by pain type) if sample size permits.

Inferential statistical methods will only be employed to highlight interesting aspects of the data. Any p-values will be interpreted descriptively; no adjustment for multiple testing to control type-1 error will be done. 95% confidence intervals (CIs) will be presented as appropriate.

Statistical analysis, data listings, graphs and summary tables will be produced using SAS®, version 9.2 or above.

